### 2.3 Secondary Objectives:

- To determine the reduction of pleural opacity (in percentage) on chest radiograph from day 1 (randomization) to day 7
- To determine the change on inflammatory markers (WBC/CRP) from day 1 (randomization) to day 7
- To determine the outcome :
  - Length of hospital stay (in days) after randomization for each group
  - The need of surgical intervention in 30 days
  - Adverse effects following t-PA/DNase and pleural irrigation
  - Mortality rate at 30 days

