### Medication Regimen :

t-PA (Alteplase) 5mg and DNase (Pulmozyme)5mg

t-PA (Alteplase) that is available in our pharmacy is 50mg ampoule and DNase (Pulmozyme) is 2.5mg per ampoule

The number of installation of intrapleural t-PA/DNase depends on the discretion of the treating physician (at least 6 hours apart between each dose). 5mg of Alteplase (t-PA) and 5mg DNase are diluted in each 50ml of 0.9% sodium chloride solution. t-PA and DNase are not mixed together in one syringe. The detailed method of t-PA/DNase therapy administration is described in Appendix 1. In brief, both medication are administered sequentially which t-PA is first instilled intrapleurally and the chest tube is then clamped for 45 minutes, then unclamped to allow free drainage for 45 minutes. The same procedure is then repeated for DNase. Selection of the timing of treatment and removal of chest tube are depending on the chest physician's judgement.

However, as for patients who were randomized into pleural irrigation group, subjects were administered 250 ml of 0.9% sodium chloride via chest tube a three way tap from a drip stand which were allowed drainage freely over 1 hour. Pleural irrigation will be performed minimum of 3 installations and maximum of 9 installation (3 times per day).

Both groups received standard care of treatment : which includes regular flushing of chest drain to maintain patency using 20mls of normal saline.

The primary outcome was to evaluate the volume of pleural effusion drainage (in mls) 72 hours following randomization. The volume drained measured after subtracting the amount of volume administered as per protocol.

The secondary outcome are measured by the change in the area of pleural opacity in chest x-ray (day 7 post t-PA/DNase compared to baseline), measured as the percentage of the ipsilateral hemithorax occupied by effusion. The area of pleural opacity and the area of the ipsilateral hemithorax will be measured digitally by two radiologists using Horos Project Software, v3.2.1 as described previously in Multicentre Intrapleural Sepsis Trial 2 (MIST-2)

Other outcomes that will be monitored include :

1. Inflammatory markers including serum C-reactive protein (CRP) & white blood count
2. Length of hospital stay in days
3. The need of surgical intervention within 30 days
4. Adverse effects :
  - a. Chest pain required escalation of analgesics
  - b. Systemic bleeding
  - c. Pleural bleeding

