During any point of treatment subjects will be allowed to cross-over and analysis will be done as per intention to treat. Subjects in the pleural irrigation group may be switched to IPFT group if there is poor response to treatment (poor drainage of effusion), or adverse effects of irrigation as per clinician's judgement. On the contrary, subjects in the IPFT group may be switched to pleural irrigation group if patient developed any adverse effects of IPFT (e.g hemothorax, haemoptysis). Those who failed both treatment will be referred for surgical intervention

Monitoring Parameters :

a. Pleural irrigation group

Parameter	Day0	Day1	Day2	Day3	Day7	Day30
Investigations						

 
• Full blood count (FBC)               
 
○ WBC
 
○ Hemoglobin
 
 
 
	√	√	√	√	√	
• C- reactive protein (CRP)	√				√	
• Chest X-ray	√				√	
• Ultrasound Thorax	√	√	√	√		
Adverse effects						
• Chest pain required escalation of analgesics		√	√	√		
• Gastrointestinal bleed		√	√	√		
• Bleeding from chest drain site		√	√	√		
• Intrapleural hemorrhage		√	√	√		
• Hemoptysis		√	√	√		
• Clinical deterioration – hypotension, dyspnea		√	√	√		
• Hb drop >10% required transfusion blood		√	√	√		
• Death related to intrapleural saline irrigation		√	√	√		

Others Outcome						
• Mortality						
• Surgical intervention						

b. IPFT group

Net Volume of pleural fluid drained (ml) post pleural irrigation	Baseline	Day 1	Day 2	Day 3
	√	√	√	√
Cumulative pleural fluid drained post pleural irrigation				√

b. Intrapleural fibrinolytic group

Parameter	Day0	Day1	Day2	Day3	Day7	Day30
Investigations						
• Full blood count (FBC) 
 
○ WBC
 
○ Hemoglobin
 
	√	√	√	√	√	
• C- reactive protein (CRP)	√				√	

• Chest X-ray	√				√	
• Ultrasound Thorax	√	√	√	√		
Adverse effects						
• Chest pain required escalation of analgesics		√	√	√		
• Gastrointestinal bleed		√	√	√		
• Bleeding from chest drain site		√	√	√		
• Intrapleural hemorrhage		√	√	√		
• Hemoptysis		√	√	√		
• Clinical deterioration – hypotension, dyspnea		√	√	√		
• Hb drop >10% required transfusion blood		√	√	√		
• Death related to intrapleural therapy		√	√	√		
Others Outcome						
• Mortality						
• Surgical intervention						

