## APPENDIX 1 :

### DRUG ADMINISTRATION OF INTRAPLEURAL t-PA (ALTEPLASE) & DNase (PULMOZYME)

Drugs dosage	Intrapleural t-PA 5mg per dose Intrapleural DNase 5mg (2 ampoules of 2.5mg) per dose at least 6 hrs apart Timing of administration: 8-9 am, 4-5 pm & next day 8-9am.	
Patient undergoing hemodialysis	No dosage adjustment provided. Suggest for heparin free dialysis while receiving t-PA and DNase	
Patient on anticoagulant	No standard guideline. Physician to assess patient's thrombotic risk & bleeding risk and decide if need to withhold anticoagulant.	
		Elimination half life
	Warfarin	20-60 hours
	Rivaroxaban	5-9 hrs ; Elderly: 11-13 hrs; renal impairment: 8.7-9.5 hrs; hepatic impairment: 10.1-10.4 hrs)
	Apixaban	~12 hrs (8-15 hrs)

	Dabigatran	12 -17 hrs; Elderly: 14-17 hrs; Mild-to-moderate renal impairment: 15-18 hrs; Severe renal impairment: 28 hrs
--	------------	---

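### Scheduled adverse-effect recording stops at Day 3 in both arms, so non-fatal events after late or rescue fibrinolytic treatment may be missed

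*Combined protocol and SAP*

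**What the plan says.** Section 2.3 lists "Adverse effects following t-PA/DNase and pleural irrigation" as a secondary objective. The schedule for collecting them is in the two Monitoring Parameters tables of section 3.6. Each has eight adverse-effect rows, covering pain, several kinds of bleeding, clinical deterioration, haemoglobin drop and treatment-related death. The last row reads "Death related to intrapleural saline irrigation" in the irrigation table and "Death related to intrapleural therapy" in the IPFT table. Every row is ticked on Days 1, 2 and 3, and none on Day 7 or Day 30. The blood count, CRP and chest X-ray rows of the same tables do carry a Day 7 tick, so lost ticks are an unlikely explanation.

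On how long treatment may last:

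- Irrigation (section 3.6, Medication Regimen): "Pleural irrigation will be performed minimum of 3 installations and maximum of 9 installation (3 times per day".
- IPFT (same section): "The number of installation of intrapleural t-PA/DNase depends on the discretion of the treating physician". Appendix 1, however, lists three times: "Timing of administration: 8-9 am, 4-5 pm & next day 8-9am".
- Cross-over (section 3.6): "During any point of treatment subjects will be allowed to cross-over", and in particular "Subjects in the pleural irrigation group may be switched to IPFT group if there is poor response to treatment". No cut-off day is given, and nothing says that the adverse-effect schedule starts again after a switch.

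Section 3.5 expects rescue IPFT after failed irrigation and names it as the probable problem of the study.

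**The concern.** The recording window is fixed in calendar days, but exposure is not. A patient can use up the whole window on irrigation and then receive a fibrinolytic, the treatment for which bleeding is the main safety question. The same applies to an IPFT patient whose course runs long at the physician's discretion. For both, the itemised checks for gastrointestinal bleeding, drain-site bleeding, intrapleural haemorrhage, haemoptysis and pain would have ended before, or just as, the relevant doses were given.

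At stake is the completeness of a stated secondary outcome in a pathway that the protocol itself foresees. Non-fatal events that nobody is prompted to record at the time are hard to recover afterwards.

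**Working it through.** The plan gives no figure to reproduce. The check compares possible treatment days with the ticked days.

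**Inputs**

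- Irrigation: 3 to 9 instillations at 3 per day (section 3.6), so 3/3 = 1 day to 9/3 = 3 days.
- Ticked adverse-effect days: 1, 2, 3 (both tables).
- IPFT: three times over two calendar days (Appendix 1).
- Start day: not fixed. Section 2.3 calls Day 1 the day of randomisation, but the tables also have a Day 0, so both are tried.
- Assumption (not in the documents): rescue IPFT starts the day after the last irrigation day and follows the Appendix 1 times.

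**Formulas**

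- Last irrigation day = start day + instillations/3 − 1.
- Rescue days = last irrigation day + 1 and + 2.
- Gap to Day 7 haemoglobin = 7 − last rescue day.

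| Start | Instillations | Last irrigation day | Rescue days | Rescue days ticked | Ticked days after last rescue dose | Gap to Day 7 haemoglobin |
|---|---|---|---|---|---|---|
| Day 0 | 3 | 0 + 1 − 1 = 0 | 1, 2 | 2 of 2 | 1 (Day 3) | 5 days |
| Day 0 | 9 | 0 + 3 − 1 = 2 | 3, 4 | 1 of 2 | 0 | 3 days |
| Day 1 | 3 | 1 + 1 − 1 = 1 | 2, 3 | 2 of 2 | 0 | 4 days |
| Day 1 | 9 | 1 + 3 − 1 = 3 | 4, 5 | 0 of 2 | 0 | 2 days |

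After a full irrigation course, at most one of the two rescue days is ticked. In three of the four cases no ticked day follows the last rescue dose. This uses the short Appendix 1 course, so it does not depend on reading section 3.6 as allowing long courses.

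For patients randomised to IPFT, an Appendix 1 course started on Day 1 occupies Days 1 and 2 and is covered, with one ticked day to follow. The gap in that arm arises only if the discretion in section 3.6 extends dosing to Day 3 or later.

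**What else could capture an event after Day 3**

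| Source | What it covers | What it leaves open |
|---|---|---|
| Day 7 blood count (tables, Appendix 1) | A fall in haemoglobin | Haemoptysis, drain-site bleeding, pain. The row for a haemoglobin drop needing transfusion itself stops at Day 3 |
| Bleeding items in the Appendix 1 observation list | Monitoring after administration | No day or duration for recording |
| Statement under Operational Definition that complications are recorded | Any complication in principle | Undated and not itemised |
| 30-day mortality with cause (section 2.3, data sheet) | Deaths | Non-fatal events |
| Data Collection Sheet grid | Has Day 7 and Day 30 columns | No instruction to complete them for adverse effects |
| Follow-up by clinic or phone | A later contact, placed at day 30 after discharge | No adverse-effect question assigned to it |

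**The case against.** The strongest reply is that the ticks do not limit what is recorded. The mortality and surgical intervention rows of the same tables carry no ticks at all, yet both are 30-day outcomes. Several undated provisions could pick up late events, and the data sheet leaves Day 7 and Day 30 open. This stands against any claim that events after Day 3 go unrecorded. It does not supply a systematic assessment: for the adverse-effect rows, the only days the protocol assigns are 1 to 3.

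A second reply is that long IPFT courses are not really planned. Appendix 1 lists three times, and section 3.8 budgets 86 DNase ampoules, or 86 × 2.5/5 = 43 doses, for an arm of about 39. The Appendix 1 point is fair, and it must be reconciled with the discretion in section 3.6. The budget is a weak guide, since three doses for each of 39 patients would already be 117. The rescue gap remains with the short course in any case.

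A third reply is that Day 4–5 rescue is a worst case, and that the schedule may restart on a switch because Appendix 1 counts some tests from treatment. The first part stands: after an early switch, both rescue days are ticked. On the second, the documents neither state nor exclude a restart, and the data sheet has a single day grid with no place for a second count.

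A reader might also infer that under-recording flatters IPFT. The documents do not support that. Under intention to treat, bleeding missed after rescue IPFT lowers the irrigation arm's count, while bleeding missed after late doses in the IPFT arm lowers that arm's count. The two pull in opposite directions, and no event or cross-over rates are given.

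**Conclusion.** The concern holds in a limited form. The itemised adverse-effect schedule ends at Day 3 in both arms and is not tied to the last intrapleural treatment. Non-fatal bleeding and other adverse effects after late or rescue IPFT are therefore not systematically scheduled for recording and may be missed. After a full irrigation course, 0 or 1 of the two rescue days is ticked, depending on whether irrigation starts on Day 1 or Day 0, assuming next-day rescue on the Appendix 1 times.

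Two stronger readings are not supported. Late events are not shown to be lost, because haemoglobin, deaths and undated complication recording give partial cover. Nor is three ticked days out of 30 a fair measure of the gap, because scheduled exposure is short and the 30-day horizon serves surgery and mortality. The number of events affected and the net direction of bias between arms cannot be determined. The point should be corrected because rescue is expected and adverse effects are a stated objective.

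**What to change.** The changes concern recording only:

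1. In both tables and on the Data Collection Sheet, assign the adverse-effect rows to Day 7 and to the existing later contact, each covering the interval since the previous assessment. State the timing of that contact consistently: the tables say Day 30, while the follow-up text says day 30 after discharge.
2. Define the recording window relative to the last intrapleural instillation, including after a switch, so that a long course or rescue treatment cannot outrun it.
3. For each event, record the date and the last intrapleural treatment given.
4. Tabulate adverse effects by randomised arm and by treatment received.
5. Define Day 0 and Day 1 once, and reconcile the section 3.6 wording on number of instillations with the Appendix 1 times.

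The cost is a small amount of extra data entry. The Day 7 tests, the clinic or phone contact and the form columns already exist, and no treatment rule changes.

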#### 3.3 Sample size and Power of Study

By using power and sample size programme calculator :

Prior data indicate that the failure rate among controls is 0.15. If the true failure rate for experimental subjects is 0.32, we will need to study 39 experimental subjects and 39 control subjects to be able to reject the null hypothesis that the failure rates for experimental and control subjects are equal with

probability (power) 0.8. The Type I error probability associated with this test of this null hypothesis is 0.5. We will use a continuity-corrected chi-squared statistic or Fisher's exact test to evaluate this null hypothesis.

N = 39+/-4 (IPFT with alteplase and DNase) and 39+/-4 (pleural irrigation with normal saline)

Study used as a reference :

Pleural irrigation trial (PIT): a randomised controlled trial of pleural irrigation with normal saline versus standard care in patients with pleural infection Clare E. Hooper, Anthony J. Edey, Anthony Wallis, Amelia O. Clive, Anna Morley, Paul White, Andrew R.L. Medford, John E. Harvey, Mike Darby, Natalie Zahan-Evans and Nick A. Maskell,

Reference for sample size taken from the primary outcome of this research in which patients receiving saline irrigation had a significantly greater reduction in pleural collection volume on computed tomography compared to those receiving standard care (median (interquartile range) 32.3% (19.6–43.7%) reduction versus 15.3% (–5.5–28%) reduction) (  $p < 0.04$ ).

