Net Volume of pleural fluid drained (ml) post IPFT	Baseline	Day 1	Day 2	Day 3
	√	√	√	√
Cumulative pleural fluid drained post IPFT				√

[figure not shown]
Operational Definition:

[figure not shown]
- Treatment success: significant amount of pleural drainage post intervention, reduction of opacity on chest x-ray and resolution of inflammatory markers on day 7 without surgical intervention within 30days
- Treatment failure:
  - Poor drainage from chest drain, failure of resolution of pleural effusion or empyema at least 50% reduction on opacity on chest x-ray and clinical evidence of ongoing infection that requires surgical intervention within 30days post randomization or death before discharge.

All patients will be followed up in respiratory clinic day 30 after discharge or phone call if patient defaulted clinic appointment.

Data will be collected prospectively (Appendix 5) by reviewed patient demographics, clinical data on length of hospital stay, pleural fluid analysis, intrapleural therapy, radiographic characteristics, adverse events, Laboratory data (blood leukocyte count, C-reactive protein, haemoglobin level), Intrapleural therapy data including number of chest tubes, duration of chest tube in pleural cavity and cumulative volume of pleural fluid drained. Besides that, length of hospital stay, treatment outcomes, surgical interventions and the occurrence of complications are recorded.

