**Outcome Monitoring:**

Parameter	Day0	Day1	Day2	Day3	Day7	Day30
Investigations						

 
• Full blood count (FBC)               
 
○ WBC
 
○ Hemoglobin
 
 
 
						
• C- reactive protein (CRP)						
• Chest X-ray						
• Ultrasound Thorax						
Adverse effects						
• Chest pain required escalation of analgesics						
• Gastrointestinal bleed						
• Bleeding from chest drain site						

• Intrapleural hemorrhage					
• Hemoptysis					
• Clinical deterioration – hypotension, dyspnea					
• Hb drop >10% required transfusion blood					
• Death related to intrapleural therapy					
Others Outcome					
• Mortality					
• Surgical intervention					

Net Volume of pleural fluid drained (ml) post pleural irrigation	Baseline	Day 1	Day 2	Day 3
Cumulative pleural fluid drained post pleural irrigation				

Other Outcome Measures	
Duration of hospital stay from 1 st dose of intrapleural t-PA/Dnase or 1 st pleural irrigation	Days
Requirement of surgical intervention within 30days from 1 st dose t-PA/DNase or 1 st pleural irrigation (normal saline 0.9%)	Yes / No  If yes, Decortication  Pneumonectomy  Lobectomy 
Outcome upon discharge	Alive  Death 
Readmission within 30 days from discharge for similar complaint (recurrent parapneumonic effusion/empyema)	Yes / No

Complete resolution on radiologically (chest x-ray) on clinic appointment	Yes / No
Mortality within 30 days (from 1 st dose intraplural t-PA/Dnase or normal saline 0.9%) & cause	

Treatment outcome	Successful 
	Failure 

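### Treatment success and failure are not complements: some patients fit neither or both, a death after discharge can score as success, and the form has only two boxes

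*Combined protocol and SAP*

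**What the plan says.** The operational definitions stand at the end of section 3.6. Success is "significant amount of pleural drainage post intervention, reduction of opacity on chest x-ray and resolution of inflammatory markers on day 7 without surgical intervention" within 30 days. Failure is not written as the absence of success. It is a list that opens with poor drainage, continues with "failure of resolution of pleural effusion or empyema at least 50% reduction on opacity on chest x-ray and clinical evidence of ongoing infection" and ends with infection that "requires surgical intervention within 30days post randomization or death before discharge".

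The Data Collection Sheet closes with a "Treatment outcome" item that has two boxes, Successful and Failure. No third category, default or adjudication rule is stated.

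Section 3.3 sizes the trial on a binary failure outcome: "Prior data indicate that the failure rate among controls is 0.15", against 0.32 in the experimental arm, to be tested by continuity-corrected chi-squared or Fisher's exact test. The only definition of treatment failure in the documents is the one in section 3.6. Section 2.3 lists "Mortality rate at 30 days" as a separate secondary outcome, and section 3.1 describes the study as open-label.

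**The concern.** A two-category outcome works only if each patient falls in exactly one category by rule. Here the two definitions use different yardsticks for opacity, infection and death, and neither drainage nor marker resolution has a numeric threshold. Someone must still tick a box for each patient the rules leave out or place twice, in a trial where treatment is known. The failure rate in each arm then depends partly on undocumented judgement and could not be reproduced from the data. A patient who dies within the 30-day window can also be reported as a treatment success.

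**Working it through.** **1. The plan's own figure.** Section 3.3 gives 39 per arm. Inputs as printed: p1 = 0.15, p2 = 0.32, power 0.8, type I error 0.5 (taken as two-sided).

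- Mean p = 0.235; z values 0.6745 and 0.8416.
- n = [0.6745·√(2·0.235·0.765) + 0.8416·√(0.15·0.85 + 0.32·0.68)]² / 0.17² = (0.4045 + 0.4944)² / 0.0289 ≈ 27.96.
- Continuity correction: (27.96/4)·[1 + √(1 + 4/(27.96·0.17))]² ≈ 38.8, so 39.

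The figure reproduces and confirms that the calculation is for a binary failure comparison. The printed 0.5 conflicts with the 0.05 in the Statistical Analysis section; that is a separate matter and is not used below.

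**2. The definitions side by side.**

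| Component | Success | Failure |
|---|---|---|
| Drainage | significant, no threshold | poor, no threshold |
| Opacity | any reduction | 50% limit |
| Infection | markers resolved at day 7 | clinical evidence, requiring surgery |
| Surgery | none within 30 days | within 30 days of randomisation |
| Death | not mentioned | only before discharge |

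**3. Three readings of failure.** The wording mixes commas, 'and' and 'or'. Death before discharge is a failure in all three.

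- (a) All clinical components must be present.
- (b) Any one component is enough.
- (c) Surgery alone decides.

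**4. Three patients under each reading.**

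- Patient A: good drainage, at least 50% reduction, markers unresolved at day 7, no surgery, alive. Not a success, because of the markers. Not a failure under (a), (b) or (c). Neither.
- Patient B: meets the success criteria, has no surgery, dies before discharge. Success has no survival condition, and the death is a failure. Both, under every reading.
- Patient C: as B, but dies after discharge within 30 days. Meets the success definition under every reading. With at least 50% reduction, C is not a failure under any of them; with 1–49%, C is also a failure under (b).

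**5. All combinations.** Drainage (2) × opacity none, 1–49% or at least 50% (3) × markers (2) × ongoing clinical infection (2) × surgery (2) × alive, dead before discharge, or dead after discharge within 30 days (3) = 144 profiles. Success holds in 1·2·1·2·1·3 = 12.

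- (a) Failure: 12 clinical + 48 deaths before discharge − 4 counted twice = 56.
- (b) Not failure: 1·1·2·3·2 = 12, where 3 is the number of infection/surgery pairs other than both present. Failure = 132.
- (c) Failure: 72 with surgery + 24 deaths before discharge without surgery = 96.

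| Reading | Success only | Failure only | Both | Neither |
|---|---|---|---|---|
| (a) | 8 | 52 | 4 | 80 |
| (b) | 4 | 124 | 8 | 8 |
| (c) | 8 | 92 | 4 | 40 |

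These are counts of logical combinations, not patient frequencies. Drainage is taken as either significant or poor, which is generous, since the text sets no boundary.

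**6. What one patient is worth.** At 39 per arm, one reclassified patient moves that arm's failure rate by 1/39 = 2.6 percentage points. The planned difference is 0.32 − 0.15 = 0.17, and 0.17·39 = 6.6 patients.

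**The case against.** Success/failure is not among the objectives (2.2, 2.3), the hypotheses (2.4), the outcomes listed in 3.6 or the Statistical Analysis section. The primary outcome is net drainage volume, and opacity, markers, surgery and mortality are each reported separately. This stands and limits the reach of the point. It does not remove it, because section 3.3 plans a test of failure rates and the form records the outcome for every patient.

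Some of the wording could be read more kindly. Section 3.4 treats raised CRP or white cell count as clinical evidence of infection. If ongoing infection and surgery were each enough on their own for failure, and raised markers counted as infection, patient A would be a failure and the gap would close. That reading has to set aside the phrase tying infection to the need for surgery. Even then the overlap remains: patient B is both, and so is a patient with a 1–49% reduction who meets every other success criterion.

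Poor drainage has an entry limit (at most 150 ml after 24 hours, sections 3.2 and 3.4), but the operational definition does not carry it over.

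A reader might infer that unblinded physicians bias the result. The documents do not say who ticks the box, opacity is measured digitally by two radiologists, and surgery and death are recorded facts. The definitions leave room for judgement; a direction of bias is not shown.

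**Conclusion.** The point holds. Under each of the three readings the definitions are neither exhaustive nor mutually exclusive, and a patient who dies after discharge within 30 days can be a success. This is a stated rule that misclassifies patients, not merely missing detail, and it should be corrected before analysis. It affects only the binary success/failure comparison.

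Three stronger inferences are not supported:

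- That the sample size rests on this definition. Section 3.3 takes its reference from the earlier irrigation trial's median CT volume reductions, 15.3% and 32.3%, which the printed 0.15 and 0.32 mirror. Repairing the definition would not repair the sample size.
- That every patient who avoids surgery with under 50% clearance or unresolved markers is unclassified. A 30% reduction with significant drainage and resolved markers meets the success definition; a 30% reduction with unresolved markers, no surgery and survival is neither under (a) and (c) but a failure under (b).
- That deaths are lost. 30-day mortality is reported on its own.

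The documents give no rate for the affected patients, so no number can be stated. The conclusion rests on the text; a tie-break rule in a figure beside the definitions would narrow it.

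**What to change.** - Define one outcome as the exact complement of the other.
- State whether the failure components are joined by 'and' or 'or'.
- Use the same opacity criterion in both. The only limit stated is 50%, and the only post-baseline film in the monitoring tables is at day 7. Say how a missing day-7 film is classified.
- Count death from any cause within 30 days as failure.
- Use one time origin. Section 3.6 counts from randomisation; the Data Collection Sheet counts from the first dose or first irrigation.
- Derive the outcome by program from the recorded opacity, surgery and mortality fields instead of a tick box.
- If drainage and inflammatory markers stay in the definition, give each a numeric threshold. If they are dropped, report them separately, as already planned. Dropping them would make patient A a success, so the choice should be deliberate and written down.

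Cost: a rewritten paragraph and a small form change. Day-7 films, 30-day surgery and 30-day mortality are already collected, and "All patients will be followed up in respiratory clinic day 30 after discharge", or by telephone, which falls later than 30 days from randomisation. The form needs the randomisation date and the dates of surgery and death. Some patients who would have been ticked as successes will count as failures.

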### 3.5 Problem Statement

Retained complicated pleural effusion is associated with a risk of empyema and sepsis. IPFT is commonly used as the bridging therapy to surgery. The efficacy of saline irrigation is not known. However, the probable problem in this study is when failed saline irrigation, the patient will be given IPFT as part of the intention to treat.

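### As printed, the success definition lets an irrigation patient rescued with IPFT for poor drainage be scored a success of irrigation

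*Combined protocol and SAP*

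**What the plan says.** Four places in the plan bear on how a switched patient is classified.

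- **Section 3.5** names the difficulty itself: "when failed saline irrigation, the patient will be given IPFT as part of the intention to treat".
- **Section 3.6, cross-over paragraph**, allows a change of treatment at any point with analysis by intention to treat. "Subjects in the pleural irrigation group may be switched to IPFT group if there is poor response to treatment", or for adverse effects, on the clinician's judgement. For the IPFT arm only adverse effects are named as a reason to switch. The paragraph ends: "Those who failed both treatment will be referred for surgical intervention".
- **Section 3.6, Operational Definition**, starts its success criteria from "significant amount of pleural drainage post intervention, reduction of opacity on chest x-ray". It then adds a laboratory and a surgical condition, worded as "resolution of inflammatory markers on day 7 without surgical intervention within 30days". The failure entry begins with drainage and imaging: "Poor drainage from chest drain, failure of resolution of pleural effusion or empyema at least 50% reduction on opacity on chest x-ray". A conjunction ties these elements to the deciding events, which are "clinical evidence of ongoing infection that requires surgical intervention within 30days post randomization or death before discharge".
- **The data collection sheet** closes with a treatment outcome field that has two boxes, successful or failure. It has no field for a switch, its date or its reason.

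The statistical analysis section gives no rule for switched patients and no sensitivity analysis.

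**The concern.** The plan uses the idea of failure in two ways. In section 3.5 and the cross-over paragraph, a patient can fail irrigation alone, and the consequence is IPFT. In the Operational Definition, failure ends in surgery or death and a switch plays no part. The same patient can therefore be failed irrigation in one section and an irrigation success in another.

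The credit runs mainly one way. An irrigation patient who responds poorly has a named route to a second intrapleural treatment before failure is scored. An IPFT patient who responds poorly has no such named route. Recorded irrigation failure is therefore lowered by the benefit of the comparator. If IPFT is truly better, the comparison is pulled toward no difference. The research question in section 2.1 is whether IPFT is superior to irrigation, so this is the direction that matters.

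**Working it through.** **Step 1: follow one patient through the text.** A patient randomised to irrigation drains poorly and is switched to IPFT within the first days. (The maximum irrigation course is 9 instillations at 3 per day, that is 9 / 3 = 3 days.) The patient then drains well, the film clears, markers resolve by day 7, and there is no surgery by day 30.

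| Place in the plan | How this patient is described |
|---|---|
| Section 3.5 | failed irrigation |
| Cross-over paragraph | poor response to irrigation; still analysed in the irrigation arm |
| Success definition | every printed element can be met |
| Failure definition | no surgery and no death, so not met if the conjunction is read as written |
| Data sheet | one of two boxes; on the printed criteria, successful |

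**Step 2: is there a plan figure to reproduce?** None exists for this outcome. The nearest is section 3.3: failure rates 0.15 and 0.32, power 0.8, 39 per arm. With the printed Type I error of 0.5 taken literally and two-sided (z = 0.6745; z for power = 0.8416; mean proportion 0.235):

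- n = (0.6745 x sqrt(2 x 0.235 x 0.765) + 0.8416 x sqrt(0.15 x 0.85 + 0.32 x 0.68))² / 0.17² = 0.808 / 0.0289 = 28.0
- with continuity correction: (28.0 / 4) x (1 + sqrt(1 + 4 / (28.0 x 0.17)))² = 38.8, rounded up to 39

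So 39 reproduces. However, section 3.3 takes its reference from median CT volume reductions of 32.3% and 15.3%, which the 0.32 and 0.15 match. They are not failure rates on the section 3.6 definition. They serve below only as convenient assumed values.

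**Step 3: illustrate the size.** Assumptions, none of them from the plan:

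- failure on irrigation alone, with a switch for poor response counted as failure: 32%
- failure on IPFT: 15%
- share of irrigation failures switched, q: 50%, 75% or 100%
- share of switched patients rescued, s: 50%, 70% or 85%. The upper end equals the assumed IPFT success rate, 100 - 15.

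Recorded irrigation failure = 0.32 x (1 - q x s). The difference is this minus 0.15.

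| q | s = 0.50 | s = 0.70 | s = 0.85 |
|---|---|---|---|
| 0.50 | 24.0% (+9.0) | 20.8% (+5.8) | 18.4% (+3.4) |
| 0.75 | 20.0% (+5.0) | 15.2% (+0.2) | 11.6% (-3.4) |
| 1.00 | 16.0% (+1.0) | 9.6% (-5.4) | 4.8% (-10.2) |

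Differences are in percentage points; without the switch effect the difference is 32 - 15 = +17. In a 39-patient arm, expected recorded failures fall from 0.32 x 39 = 12.5 to between 0.24 x 39 = 9.4 and 0.048 x 39 = 1.9.

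The sign reverses only if q x s exceeds 1 - 0.15 / 0.32 = 0.53, that is, if more than about 53% of all irrigation failures are both switched and rescued.

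**The case against.** **Intention to treat is a deliberate choice.** The plan foresees rescue and states how it will analyse. Scoring final outcome in the randomised arm is a legitimate comparison of starting with irrigation against starting with IPFT. This stands, and it is why the printed scoring should be kept. It does not remove the need to say which question that scoring answers.

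**The wording leaves room.** The drainage element of success follows an unspecified intervention, which could mean the allocated one only. Poor drainage, listed first under failure, could be read as sufficient alone, although the conjunction ties it to infection needing surgery. This stands in part: misclassification is what the printed wording permits, not what every scorer would do. A rescued patient must also meet the day-7 criteria and avoid surgery. Two defensible scorings of one patient in an open-label trial are still a reason to settle the text beforehand.

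**The outcome is not a listed endpoint.** Success/failure does not appear in the objectives, the hypotheses or the outcome list in section 3.6. It is an operational definition and a field on the sheet. This stands and limits the severity.

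**A reader might infer that the trial is sized on this outcome,** because section 3.3 speaks of failure rates. The documents do not support that. Section 3.3 draws on CT volume reductions and never refers to the section 3.6 definition.

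**Counting a switch as failure could bias the other way.** By rule, only irrigation patients can switch for poor response, and the decision is unblinded and has no stated volume or time threshold. This stands, and the fix has to deal with it.

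**The flow chart is not reproduced in the text available.** If it contains a rule for switched patients, that rule should be carried into the definition.

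**Conclusion.** The point holds as an inconsistency between the success/failure definition and the plan's own account of failed irrigation, and its effect has a clear direction. On the printed wording, an irrigation patient rescued with IPFT for poor drainage can be scored a success of irrigation. The resulting comparison describes starting strategies and does not alone answer the question in section 2.1.

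The size is unknown, because the documents give no switch or rescue rates. Under the assumptions above, a 17-point difference becomes anything from +9 to about -10 points.

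Two stronger conclusions are tempting and are not supported. One is that the comparison will reverse in favour of irrigation. That needs more than about 53% of irrigation failures to be switched and rescued, whereas the plan only permits switching; with half switched, no rescue rate up to 85% reverses it. The other is that the trial cannot answer its question at all. The primary outcome is drained volume, and this point does not concern that analysis. It should be fixed, but it does not undermine the primary comparison.

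**What to change.** - **Section 3.6, Operational Definition:** state that a patient switched to the other intrapleural treatment for poor response is not a success of the allocated treatment.
- **Data collection sheet:** record the date and reason of every switch, so that switches for adverse effects are kept apart from those for poor response. Replace the two outcome boxes with three: success on allocated treatment, resolved after switch, failure.
- **Statistical analysis section:** report two comparisons, both by randomised arm. The first uses the printed definition, labelled as the result of the starting strategy. The second is failure of allocated treatment, meaning printed failure or a switch for poor response.
- **For the second comparison,** score poor drainage in both arms by one criterion, stated in advance and based on the daily net volumes that the section 3.6 monitoring tables already require for each arm. Otherwise the added event is one that only irrigation patients can have. The investigators need to set that criterion.

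The change affects scoring only, not who is switched or when. The cost is a short addition to the definition, a few fields on the sheet, one agreed scoring criterion and one extra table. The drawback is that the switch remains an unblinded clinical decision, so neither version should be shown without the other.
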